In phase II, the feasibility and efficacy of long-term (5 week) self-administration of the tDCS intervention will be evaluated in concurrence with self-administered cognitive stimulation. In this phase the research participants will be taught to use the mobile tDCS device and will be provided with one to take home. The device will be programmed by the investigators in advance to control the intensity and duration of the stimulation. The research participants will use the device twice per week as directed. Before each session, the participant will use an institutionally provided iPad for video conferencing with the study center to obtain a unique access code to start the tDCS device and ensure proper device placement. Each stimulation session for each participant will have a unique access code. An AE evaluation will be conducted by a trained study team member every week. Research participants will complete remote neurocognitive testing via the iPad before and after phase II.

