#### **4.2.2 Transcranial Direct Current Stimulation – Mobile System:**

The mobile transcranial direct current stimulation system is manufactured by Soterix Medical and consists of a battery pack, control unit and a self-positioning headband with sponges. Participants will be given the device after completing the clinical portion of the study and trained in correct usage. Participants will complete two stimulation sessions per week for 5 weeks. The sessions will provide 1 mA DC for 15 minutes in the same manner as the clinical system. Participants will be supplied iPads for the cognitive stimulation training, and the iPad will be used to monitor correct tDCS usage. The tDCS unit requires a unique code for each stimulation session. Study staff will use video conferencing to confirm correct electrode placement, then provide the code to initiate treatment. Each session will be monitored for compliance and to assess any adverse events.

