#### **4.3 Adverse Event Monitoring:**

Reports of adverse events will be monitored. Adverse events will be surveyed at the beginning of each video conference, with symptoms reports for the prior stimulation session. Adverse event information will be collected by participant reporting and direct questioning using the patient report of incidence of side effects (PRISE), frequency and intensity of side effect rating (FISER), and global rating of side effects burden (GRSEB). The PRISE form assesses the presence of side effects for a variety of biological systems. For each of the nine organ/function systems (gastrointestinal, nervous system, heart, eyes/ears, skin, genital/urinary, sleep, sexual functioning, and other), the participant indicates the presence of a side effect, and if present, the tolerability of the side effect (tolerable or distressing). The FISER and GRSEB assess three domains of side effect impact: frequency, intensity, and burden. Each domain is rated on a 7-point Likert scale (i.e. Frequency, ranging from no side effects to present all the time; Intensity, ranging from no side effects to intolerable; and Burden, ranging from no impairment to unable to function due to side effects). Reliability and validity have been reported.

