## **7 SAFETY AND ADVERSE EVENT REPORTING REQUIREMENTS**

### **7.1 Reporting Adverse Experiences and Deaths to St. Jude IRB**

**Only “unanticipated problems involving risks to participants or others” referred to hereafter as “unanticipated problems” are required to be reported to the St. Jude IRB promptly, but in no event later than 10 working days after the investigator first learns of the unanticipated problem.**

**Regardless of whether the event is internal or external (for example, an IND safety report by the sponsor pursuant to 21 CFR 312.32), only adverse events that constitute unanticipated problems are reportable to the St. Jude IRB. As further described in the definition of unanticipated problem, this includes any event that in the PI's opinion was:**

- Unexpected (in terms of nature, severity, or frequency) given (1) the research procedures that are described in the protocol-related documents, such as the IRB-approved research protocol and informed consent document, as well as other relevant information available about the research; (2) the observed rate of occurrence (compared to a credible baseline for comparison); and (3) the characteristics of the subject population being studied; and
- Related or possibly related to participation in the research; and
- Serious; or if not serious suggests that the research places subjects or others at a greater risk of harm (including physical, psychological, economic, or social harm) than was previously known or recognized.

Unrelated, expected deaths do not require reporting to the IRB. Though death is “serious”, the event must meet the other two requirements of “related or possibly related” and “unexpected/unanticipated” to be considered reportable.

Deaths meeting reporting requirements are to be reported immediately to the St. Jude IRB, but in no event later than 48 hours after the investigator first learns of the death.

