**Unexpected Adverse Event:**

- Any adverse event for which the specificity or severity is not consistent with the protocol-related documents, including the applicable investigator brochure, IRB approved consent form, Investigational New Drug (IND) or Investigational Device Exemption (IDE) application, or other relevant sources of information, such as product labeling and package inserts; or if it does appear in such documents, an event in which the specificity, severity or duration is not consistent with the risk information included therein; or
- The observed rate of occurrence is a clinically significant increase in the expected rate (based on a credible baseline rate for comparison); or
- The occurrence is not consistent with the expected natural progression of any underlying disease, disorder, or condition of the subject(s) experiencing the adverse event and the subject's predisposing risk factor profile for the adverse event.

**Internal Events: Events experienced by a research participant enrolled at a site under the jurisdiction of St. Jude IRB for either multicenter or single-center research projects.**

**External Events:** Events experienced by participants enrolled at a site external to the jurisdiction of the St. Jude Institutional Review Board (IRB) or in a study for which St. Jude is not the coordinating center or the IRB of record.

**Unanticipated Problem Involving Risks to Subjects or Others:** An unanticipated problem involving risks to subjects or others is an event which was not expected to occur and which increases the degree of risk posed to research participants. Such events, in general, meet all of the following criteria:

- unexpected;
- related or possibly related to participation in the research; and
- suggests that the research places subjects or others at a greater risk of harm (including physical, psychological, economic, or social harm) than was previously known or recognized. An unanticipated problem involving risk to subjects or others may exist even when actual harm does not occur to any participant.

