## **8.2 Study Monitoring**

The study team will hold monthly meetings and review case histories or quality summaries on participants. The PI and study team will be responsible for ensuring protocol compliance. Continuing reviews by the IRB and CT-SRC will occur at least annually.

This study is associated with an Investigational Device Exemption (IDE) and will be monitored by the St. Jude Clinical Research Monitors accordingly. The monitors will review up to 15% of the study participants semi-annually for appropriateness of the informed consent process, eligibility, adverse event recording and participant's status. Additional information may be monitored at the request of the Internal Monitoring Committee (IMC), the IRB, or other institutional administration.

Source document verification of eligibility and informed consent for 100% of St. Jude participants will be performed by the Eligibility Coordinators within 5 working days of completion of enrollment. The Clinical Research Monitor will review all SAE reports and other applicable essential regulatory documentation. The Monitor will generate a formal report which is shared with the Principal Investigator (PI), study team, and the Internal Monitoring Committee (IMC).

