### **Analysis:**

Objective 1.1.1: The feasibility of the 5-week tDCS intervention will be evaluated using Simon's two stage Minimax design with stopping rules described above.

Objective 1.2.1: The improvement in scores on symbol digit coding, Stroop test, shifting attention test, digit span and verbal fluency from baseline to 5-week follow up will be done using matched pair one sample t-tests. In addition, the improvement in EF measures over the 5 week period will also be evaluated using longitudinal methods and implemented using PROC MIXED or PROC GEE in SAS 9.3.

Objective 1.2.2: The improvement in the scores on the NIH Toolbox Card Sort, Flanker and Working Memory tasks between tDCS and sham, will be done using matched pair one sample t-test.

It will be important to monitor for AEs in both phases of the study as well. Thus, in an "ad hoc" manner using one sided 95% confidence bounds we will monitor for all grade 3 or higher adverse events (All types of AE's included)

which are related to study interventions. Among the 45 patients enrolled in the study, if at any time point at least 5 patients ( $\geq 5$ ) have grade 3 or higher toxicity, the 95% lower confidence limit would be 0.059 suggesting that the true AE rate could be higher than 5% which would be unacceptable, the feasibility of the 5 week intervention would be questionable and a consideration will be given to stop or amend the trial.

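### The only numeric aggregate trigger for related grade 3+ adverse events is a fixed count of 5 patients; its supporting limit of 0.059 does not reproduce, and smaller early clusters can already meet the plan's own 5% criterion

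*Combined protocol and SAP*

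**What the plan says.** Under Analysis in Section 9, the plan states that "using one sided 95% confidence bounds we will monitor for all grade 3 or higher adverse events", limited to events related to the study interventions, and calls this monitoring ad hoc. The action rule follows: "Among the 45 patients enrolled in the study, if at any time point at least 5 patients" have such toxicity, the lower limit would be 0.059, the true rate could exceed an unacceptable 5%, and stopping or amending is to be considered. The interval method is not named, and no count is given for fewer than 45 patients.

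Other sections provide safeguards without an aggregate number:

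- **Detection.** Section 4.1: "An AE evaluation will be conducted by a trained study team member every week". Section 4.2.2: "Each session will be monitored for compliance and to assess any adverse events". Section 4.3: "Adverse events will be surveyed at the beginning of each video conference".
- **IRB reporting.** Section 7.1 requires unanticipated problems to be reported promptly, "in no event later than 10 working days after the investigator first learns of the unanticipated problem". Its definition of an unexpected event includes a rate criterion, "The observed rate of occurrence is a clinically significant increase in the expected rate", with no figure attached.
- **Protocol changes and toxicity review.** Section 7.1 also says that unanticipated problems generally warrant considering substantive protocol changes, and it sets toxicity monitoring every six months.
- **Study review.** Section 8.2: "The study team will hold monthly meetings and review case histories or quality summaries on participants". Monitor reports go to the Internal Monitoring Committee.
- **Individual withdrawal.** Section 6.1.5 lets the PI take a participant off study if continuing would be harmful.

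**The concern.** A criterion based on a confidence bound depends on the number of events and the number of patients together. A single count worked out at full enrolment is too high when few patients have been treated. A cluster of 2, 3 or 4 related grade 3+ events early on can put the bound above 5% and still leave the only written number unmet.

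The text can also be read as the method worked through at n = 45, with bounds available to the team at any earlier point. On that reading the interim thresholds are simply unwritten, and the method cannot be recovered from the one printed limit because that limit does not reproduce. Two statisticians could then disagree about the same data.

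At stake is how soon a prompt to reconsider the trial appears. Later participants self-administer stimulation at home under remote observation.

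**Working it through.** **Inputs, all from Section 9:** one-sided 95% bound; unacceptable rate 5%; trigger 5 patients; 45 enrolled; stated limit 0.059; Simon first stage of 23.

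**1. The plan's own figure, 5 of 45.** The exact (Clopper-Pearson) lower limit L solves P(X ≥ x | n, L) = 0.05, which is the 5% quantile of Beta(x, n − x + 1). For x = 5 and n = 45 this is Beta(5, 41), giving 0.0448. As a check, P(X ≥ 5 | 45, 0.05) = 0.0729, which is above 0.05, so the exact limit must lie below 5%. Other one-sided methods give:

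- Jeffreys: 0.0521
- Wilson: 0.0551
- Wald: 0.1111 − 1.645 × √(0.1111 × 0.8889 / 45) = 0.0341

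None gives 0.059. The exact limit for 6 of 45 is 0.0597.

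**2. Where the exact limit crosses 5%.**

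| Events | Largest n with limit above 5% | Limit there | Limit at n + 1 |
|---|---|---|---|
| 2 | 7 | 0.0534 | 0.0464 |
| 3 | 16 | 0.0531 | 0.0499 |
| 4 | 28 | 0.0503 | 0.0485 |
| 5 | 40 | 0.0506 | 0.0493 |

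Hand check for 2 events: P(X ≥ 2 | 7, 0.05) = 1 − 0.95^7 − 7 × 0.05 × 0.95^6 = 1 − 0.6983 − 0.2573 = 0.0444, below 0.05. At n = 8 it is 1 − 0.6634 − 0.2793 = 0.0572, above 0.05.

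**3. Dependence on method.** The boundaries in step 2 are specific to the exact method. Under Wald, 2/7 gives 0.005, 3/16 gives 0.027 and 4/28 gives 0.034, all below 5%. That some cluster smaller than 5 meets the criterion is not specific to one method: 3 in 11 exceeds 5% under exact (0.079), Jeffreys (0.106), Wilson (0.115) and Wald (0.052).

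**4. Chance of firing.** This is an exact binomial recursion over n = 1 to 45. It compares the fixed count of 5 with a table of 2 (n up to 7), 3 (8–16), 4 (17–28) and 5 (29–45). It assumes independent patients, a constant rate, and each outcome known when the patient is counted. Each cell shows fixed count versus table.

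| True rate | Review | By patient 23 | Whole trial |
|---|---|---|---|
| 5% | each patient | 0.5% vs 7.5% | 7.3% vs 12.4% |
| 5% | every 5 | 0.3% vs 5.2% | 7.3% vs 10.6% |
| 5% | every 10 | 0.3% vs 2.2% | 7.3% vs 8.1% |
| 10% | each patient | 7.3% vs 30.2% | 47.3% vs 53.9% |
| 10% | every 10 | 4.3% vs 15.3% | 47.3% vs 48.5% |
| 20% | each patient | 49.9% vs 77.6% | 96.2% vs 96.9% |
| 20% | every 10 | 37.0% vs 61.0% | 96.2% vs 96.3% |

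With per-patient review at a 20% rate, the median trigger is patient 24 versus patient 12. At a 2% rate the whole-trial figures are 0.2% versus 1.2%.

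**The case against.** A reader might infer that an early cluster would go unnoticed, or that nothing short of 5 patients could prompt a change. The documents do not support that. Sections 2.2 and the Human Subjects overview anticipate only mild effects, so a related grade 3+ event would usually be unexpected in severity. If it is also serious, or suggests greater risk than was known, Section 7.1 sends it to the IRB, and a single such event generally warrants considering protocol changes. That consequence is close to the one attached to the count of 5. This objection stands. It limits the gap to a numeric aggregate threshold, which matters most for related grade 3+ events that do not qualify as unanticipated problems.

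The per-patient figures are a best case. The stated toxicity review is six-monthly, and the monthly meetings permit more frequent looks. No accrual rate is visible, so patients per look cannot be worked out. With review every 10 patients, whole-trial detection at a 10% rate barely moves (47.3% versus 48.5%). This also stands, and it is why the benefit is described as timing.

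True rates of 10% and 20% are illustrative. The meta-analysis cited in Section 2.2 reported nothing beyond mild events, and at a 2% rate either rule rarely fires.

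Finally, the ad hoc wording allows bounds to be computed early. It does, but with no method, threshold or schedule below 5 patients.

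**Conclusion.** The point holds in a limited form and is worth considering, with moderate confidence. The printed limit of 0.059 for 5 of 45 is not reproduced by any standard method tried; the exact value is 0.0448. The single count also leaves early clusters that meet the 5% criterion without a numeric aggregate trigger. The specific boundaries rest on choosing exact limits, which the plan does not name.

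The benefit is an earlier prompt. At a true 20% rate, the table adds 24 to 28 percentage points to the chance of firing by patient 23 (61.0 − 37.0 and 77.6 − 49.9), depending on review frequency. Whole-trial detection barely changes.

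A reader might also infer from 0.0448 that the trigger at full enrolment should rise to 6. That does not follow. The rule is non-binding, a count of 5 is the more protective choice, and raising it to 6 at n = 41–45 within the table would lower whole-trial detection at a 20% rate to 95.2% with per-patient review, below the 96.2% of the present rule.

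**What to change.** In Section 9, replace the single count with a non-binding table of participants with related grade 3+ events:

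| Participants who have started at least one Phase I stimulation session (active or sham) | Consider stopping or amending at |
|---|---|
| up to 7 | 2 |
| 8–16 | 3 |
| 17–28 | 4 |
| 29–45 | 5 |

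Counting anyone who has started a session, active or sham, avoids unblinding a participant who stops after day 1. Name the exact (Clopper-Pearson) method, and tie the review to an existing schedule such as the monthly meetings. Correct 0.059 to 0.0448 for 5 of 45, and state that 5 is kept at n = 41–45 as a deliberately more protective choice. Leave the consequence as it is. At the same looks, this table fires whenever the present count would.

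The cost is one table and a few sentences, with no added patients or data. The downside is more non-binding false signals at a true 5% rate: 12.4% over the trial with per-patient review, 10.6% with review every 5 patients and 8.1% every 10, against 7.3% now. If that is too many, starting at 3 for n up to 16 gives 10.4% with per-patient review. That version gives up the trigger at 2 events in up to 7 patients, and firing by patient 23 at a 10% rate falls from 30.2% to 26.1%.

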## **9 STATISTICAL CONSIDERATIONS**

The sample size justification will be based on evaluating the primary objective, as that objective is the basic design of how the intervention will be delivered in a subsequent randomized controlled trial should this pilot study prove feasible. We will consider the trial to be feasible if at least 50% of the survivors are able to complete 5 sessions (tDCS along with cognitive stimulation) successfully out of 10. Any participant who completes Phase I,

but is unwilling to participate in Phase II due to the tDCS procedure will be counted towards failure. In the testing of hypothesis framework we would like to test the null hypothesis  $H_0: P \leq 0.5$  vs.  $H_1: P > 0.7$ . Then, using Simon's two-stage Minimax design with type I error rate  $\alpha=0.05$  and power  $(1-\beta)=0.8$  we have the following stopping rules. As an additional measure of feasibility, the consent rate must be  $>50\%$  among all participants approached to participate. Study staff will track study enrollment, and the study statistician will make the determination for study continuation.

In the first stage we will recruit 23 survivors and if the number of survivors who complete at least 5 sessions is at least 13 then we will proceed to the next stage and recruit an additional 14 survivors and if at least 24 survivors out of 37 complete at least 5 sessions then the tDCS trial would be considered feasible. However, since we expect that roughly 20% of the survivors may not initiate the trial after leaving the institution (i.e. may not provide any information at all for objective 1.1.1) we anticipate replacing these survivors and, thus, a total of 45 survivors will be needed for evaluating the Phase II objective. Participant accrual will cease when 37 participants agree to participate in Phase II.

With 37 survivors recruited for phase I of the study, we will have roughly 97.7% power for objective 1.2.1 to detect an improvement of 0.65 in standardized units, respectively, with type I error  $\alpha=0.05$ .

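### The lower confidence limit behind the adverse event trigger is wrong: 5 of 45 gives an exact one-sided 95% limit of 0.045, not 0.059

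*Combined protocol and SAP*

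**What the plan says.** The last paragraph of the Analysis part of section 9 (Combined protocol and SAP) sets out the safety monitoring. It covers both phases and counts events of any type that are related to the study interventions: "using one sided 95% confidence bounds we will monitor for all grade 3 or higher adverse events". The text calls this monitoring ad hoc.

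The denominator and the trigger are explicit: "Among the 45 patients enrolled in the study", and "if at any time point at least 5 patients" have grade 3 or higher toxicity. The justification follows: "the 95% lower confidence limit would be 0.059 suggesting that the true AE rate could be higher than 5" per cent, a rate the plan regards as unacceptable. Once the trigger is reached, "a consideration will be given to stop or amend the trial".

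The plan does not name the method for the confidence limit.

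**The concern.** The count of 5 is presented as the point at which the lower confidence limit lies above 5%, with a visible margin (0.059 against 0.05). If the limit for 5/45 is in fact below 5%, the stated reason for the trigger fails under the standard exact method. The people who review events at the trigger would then be reading a wrong number as their evidence.

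They also could not tell what the count of 5 is meant to do. It could be a demonstration that a 5% rate has been excluded, or an early prompt to look.

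**Working it through.** **Inputs, all from the Analysis part of section 9:** trigger count x = 5; denominator n = 45; one-sided 95% confidence, so 0.05 in the lower tail; stated limit 0.059; unacceptable rate 5%.

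**1. Attempt to reproduce 0.059 by the exact method.** The one-sided 95% Clopper-Pearson lower limit is the rate p at which P(X ≥ x | n, p) = 0.05. This is the 0.05 quantile of a Beta(x, n − x + 1) distribution.

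- 5/45: BetaInv(0.05; 5, 41) = **0.0448**.
- Check: P(X ≥ 5 | n = 45, p = 0.0448) = 0.050, as required. At p = 0.059 the same tail is 0.124, so 0.059 is not a 95% limit for 5/45.

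**2. Attempt to reproduce it by other methods.** All are one-sided 95% limits for 5/45.

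| Method | Lower limit | Above 5%? |
|---|---|---|
| Wald | 0.034 | no |
| Poisson | 0.044 | no |
| Exact | 0.045 | no |
| Arcsine | 0.0465 | no |
| Wilson, continuity-corrected | 0.048 | no |
| Complementary log-log | 0.0492 | no |
| Likelihood ratio | 0.0497 | no |
| Mid-P | 0.0505 | yes |
| Jeffreys | 0.052 | yes |
| Agresti-Coull | 0.052 | yes |
| Logit | 0.054 | yes |
| Wilson | 0.055 | yes |
| Log | 0.0555 | yes |
| Uniform-prior Bayes | 0.0584 | yes |
| Plus-four | 0.0606 | yes |

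As a worked line, Wald is 5/45 − 1.645 × √(0.1111 × 0.8889 / 45) = 0.1111 − 0.0771 = 0.034.

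None of these rounds to 0.059. Changing the confidence level does not help the exact method: 5/45 gives 0.0371 at one-sided 97.5% and 0.0550 at one-sided 90%.

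**3. Where 0.059 might come from.** The exact limit for 6/45 is BetaInv(0.05; 6, 40) = 0.0597, which becomes 0.059 if truncated. A slip between "5 or more" and "more than 5" would produce it. This is an inference, and the documents do not confirm it.

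**4. What the trigger does at 45 patients.** At a true rate of 5%, the binomial probabilities of 0, 1, 2, 3 and 4 events are 0.0994, 0.2355, 0.2727, 0.2057 and 0.1137. Before rounding they sum to 0.9271, so P(X ≥ 5) = 1 − 0.9271 = 0.073. This is above the 0.05 that a one-sided 95% bound implies.

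| True rate | P(5 or more of 45) | P(6 or more of 45) |
|---|---|---|
| 5% | 7.3% | 2.4% |
| 10% | 47.3% | 29.2% |
| 15% | 82.5% | 68.6% |

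**5. Smaller denominators.** The rule applies at any time point, but the limit is worked out only for 45.

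- Five events have an exact limit above 5% up to n = 40 (0.0506). At n = 41 the limit is 0.0493.
- Smaller counts can also exceed 5% early without reaching 5: 3/10 gives 0.087 and 4/23 gives 0.062.

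**The case against.** The strongest reply is that nothing operational depends on the wrong number. Staff apply the count, not the limit. The count of 5 is more cautious than the 6 that the exact limit supports, and reaching it leads only to a discussion. That stands, and it limits the weight of the point.

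A second reply is that the plan only says the rate *could* exceed 5%, which is true of 5/45 (11.1% observed) on any method. This is fair as far as the wording goes. But quoting a lower limit above 5% implies that 5% has been excluded, and by the exact method it has not.

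A third reply is that several common methods do place 5/45 above 5%, and that the exact limit also does so for up to 40 patients. Both statements are correct. Neither rescues 0.059, which the plan ties to 45 patients, and the dependence on method is a reason to name one.

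Finally, a fixed count is a legitimate simple rule for a pilot. Toxicities are also reviewed every six months (section 7.1), and there are monthly team meetings, clinical research monitors and an Internal Monitoring Committee (section 8.2). A table of interim counts is therefore a design choice and not a correction of an error.

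**Conclusion.** The concern holds. The stated limit of 0.059 is wrong for 5 of 45 at one-sided 95% confidence. The exact value is 0.0448, and no standard method tried gives 0.059. That the figure is wrong does not depend on which of those methods is chosen. Whether 5/45 clears 5% does depend on it: by the exact method it does not, and the smallest count that does is 6.

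The result assumes the inputs as written and, for the trigger probabilities, independent patients with a common event rate and all 45 enrolled. This is a moderate correction to the stated basis of the plan's only numeric safety trigger. It is not a safety failure, because the error leaves a trigger that acts earlier than the exact limit would support.

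**What to change.** **Recommended.** State that the limit is the exact (Clopper-Pearson) one-sided 95% limit, and replace 0.059 with 0.045 for 5/45. Keep the trigger at 5 or more. Describe it as deliberately cautious, with a 7.3% chance of being reached by 45 patients at a true rate of 5%, and not as evidence that the rate exceeds 5%. This is a one-sentence text change that alters no count and adds no patients, visits or procedures.

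**Alternative.** Move the trigger to 6 or more, with an exact limit of 0.060. The chance of triggering at a true 5% rate falls to 2.4%. The cost is a later prompt: 29.2% against 47.3% at a true rate of 10%. Keeping 5 is preferable because it is more protective.

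**Optional.** If the sponsor wants the bound to apply throughout accrual, add the smallest counts whose exact limit exceeds 5%: 2 for up to 7 treated, 3 for 8–16, 4 for 17–28 and 5 for 29–40, keeping 5 for 41–45. Checked after every patient, this prompts review with probability 12.4% at a true rate of 5% and 53.9% at 10%. Those figures should be stated if the table is adopted.
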